In summary, hysteroscopic surgery is the most effective treatment for patients with large retained products of conception. However, due to the large size of the lesion, especially in cases of a large uterus, high serum HCG levels, and rich blood supply, the likelihood of needing repeat or even multiple curettage procedures increases, raising the risk of infection and endometrial damage. This not only increases costs but also leads to intrauterine adhesions and infertility. For these patients, appropriate drug treatment or expectant management followed by hysteroscopic surgery may be a wise choice and warrants further clinical research. Drug treatment and expectant management are also effective and safe under certain conditions for managing retained products of conception. Previous studies have shown that expectant management can allow some patients to expel the retained products of conception spontaneously, avoiding curettage; when curettage is performed 1-3 months after termination of pregnancy, serum HCG levels drop to low levels, reducing the difficulty of hysteroscopic surgery, intraoperative risks, and the likelihood of repeat surgery, as well as the incidence of postoperative intrauterine adhesions. Therefore, we propose the following scientific hypothesis: for patients with retained products of conception, in the absence of infection and active bleeding, expectant management should be maintained until the appropriate surgical time, thereby reducing the likelihood of repeat surgery and protecting the endometrium. To verify this scientific hypothesis, we designed a prospective, observational, multicenter, real-world study. The study subjects were patients with retained products of conception without bleeding or infection. Under the guidance of the physicians in the treatment group and with full informed consent, patients were selected according to their wishes to either the active surgery group (control group) or the expectant management group (study group). The diagnosis and treatment procedures were standardized, and detailed clinical data were collected to explore the optimal treatment strategy for retained products of conception, especially the best treatment plan for the protection of fertility.

II. Research Objectives

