4.1.2 Expectant Treatment Group

1) In the outpatient clinic, complete routine examinations of vaginal secretions, blood β -HCG, complete blood count, CRP, procalcitonin (optional), chlamydia and gonococcus, and other infection indicators. If the 4D color ultrasound indicates placenta accreta or retained products of conception in special locations such as the uterine horn or cesarean section incision site (CSP), and if necessary (especially when CSP or interstitial retained products of conception cannot be ruled out), complete a pelvic MRI plain scan with contrast. At the same time, complete liver and kidney function tests and coagulation function tests.

2) For patients without contraindications, administer 2mg of Progynova twice daily (or a similar dose of Estradiol) until postoperatively (generally, continue using Progynova for 2-4 weeks postoperatively with progesterone withdrawal bleeding); then

discontinue oral administration of Leonurus japonicus granules or Acanthopanax senticosus capsules for 2 weeks.

4D color Doppler ultrasound of the uterus and adnexa every 2-3 weeks ; until **the predetermined surgical timing is reached** : 1) Blood β -HCG <50mmol / L; 2) Ultrasound measurement of the length from the internal cervical os to the fundus \leq 6cm; 3) At least 4 weeks between the previous surgery; 4) Color Doppler ultrasound showing blood flow grade 1-3 at the pregnancy tissue and attachment site . This predetermined surgical timing is proposed based on our hospital's summary of previous patient data and literature analysis. Research hospitals can adjust the surgical timing parameters according to clinical experience. Patients who reach the predetermined surgical timing will be hospitalized, undergo relevant examinations, and undergo hysteroscopic removal of the pregnancy tissue (hysteroscopic surgery using a large cold knife instrument is recommended ; refer to the surgical video).

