4.2.3 Postoperative management

Prevention of intrauterine adhesions: 1) **Inject sodium hyaluronate gel (Gongankang or Yishukang)** into the uterine cavity according to the uterine depth (2-3 ml for a uterine depth of 7 or 8 cm , 5 ml for a uterine depth of 10 cm). 2) If necessary, leave the uterine balloon in place for 48-72 hours and remove it. If there are adhesions in the lower segment of the uterine cavity, part of the internal cervical os, or complete adhesions, handle them according to the intraoperative situation; adjust the amount of water injected into the balloon according to the uterine depth (3 ml for a uterine depth of 7-8 cm, 3.5 ml for a uterine depth of 9 cm, and 4 ml for a uterine depth of 10 cm) . 3) If there are no contraindications, administer 2 mg BID of estradiol valerate (or an equivalent dose of estradiol) orally for 21-28 days postoperatively. (For patients with serum β -HCG levels not typically associated with pregnancy, oral administration until 21 days post-surgery; for patients with β -HCG levels above 100 mmol /L, oral administration until 28 days post-surgery). For the following 6 days, add progesterone (or dydrogesterone) 200 mg orally before bedtime. Continue for a total of two menstrual cycles. Adjustments may be made based on the condition of patients with other intrauterine diseases.

Treatment to promote uterine contraction: routine intravenous administration of uterine contraction agents (ostomycin is routinely used, and ergonovine may be used if necessary) for 48 hours after surgery; oral administration of uterine contraction-promoting drugs (such as *Acanthopanax senticosus* capsules, etc.) for 2 weeks.

Infection prevention: If there are signs of infection or high-risk factors for infection, antibiotics may be used as appropriate, and the type of antibiotic, route of administration, dosage, frequency and duration of administration should be recorded accurately.

Pathological examination: The pregnancy tissue removed during the operation is routinely sent for pathological examination. If endometritis is suspected, endometrial tissue can be sent for immunohistochemical examination of CD138. CNVs can be performed if genetic testing is required.

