Postoperative follow-up indicators: β -HCG on the 3rd day after surgery (once a week thereafter until normal), complete blood count (days 1 and 3), CRP, procalcitonin (not mandatory); if necessary, transvaginal ultrasound on the 2nd-3rd day after surgery. A 4D ultrasound is performed on days 16-24 of the third menstrual period after surgery to assess the uterine cavity and blood flow (report templates are available, mainly assessing damage to the endometrium).

Management of retained products of conception after surgery: If ultrasound shows that the diameter of the retained products of conception is less than 0.5 cm, an artificial cycle is given, and a follow-up color Doppler ultrasound and β -HCG test are performed after the next menstrual period to determine whether further surgery is needed; if ultrasound shows that the diameter of the retained products of conception is greater than 0.5 cm, the patient is put back into the expectant management process and managed as an outpatient.

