5.2 Preoperative data on retained products of pregnancy: gestational age at termination; time of termination; serum β -HCG; imaging data (including ultrasound and MRI: uterine size, distance from the internal cervical os to the fundus, location of the retained products of pregnancy, maximum diameter, blood flow, presence of arteriovenous fistula (blood flow grade 1-6 in the retained products of pregnancy and surrounding uterine wall on color Doppler ultrasound), presence of placenta accreta, presence of intrauterine adhesions, uterine septum, uterine fibroids, adenomyosis. For the expectant management group, complete blood count, serum β -HCG, CRP, and ultrasound data from each follow-up examination should be collected.

5.3 Preoperative routine examination data : routine vaginal discharge test, HPV/TCT, complete blood count, liver and kidney function tests, electrolytes, coagulation function tests, thyroid function tests, serum β -HCG, anti-Müllerian hormone test, pre-transfusion examination, electrocardiogram, chest X-ray, 3D color Doppler ultrasound of the uterus and bilateral adnexa, and other relevant examinations. If a 3D ultrasound has been completed within one week in the outpatient clinic, it does not need to be repeated during hospitalization.

5.4 Surgical data: Date of surgery; depth of uterus; location and size of the gestational sac; operation time (from the start of the distension procedure to the withdrawal of the endoscope); amount of intraoperative blood loss; whether there is any retained gestational sac after surgery; clarity of the surgical field; volume of distension fluid in and out; whether there is a decrease in blood oxygen saturation;

whether complications such as uterine perforation, acute left heart failure, or gas embolism occur.

5.5 Postoperative follow-up data: serum β -HCG, complete blood count, CRP, procalcitonin (not required), ultrasound to check for retained products of conception, and if so, record the maximum diameter of the retained products.

5.6 Three months after treatment , outpatient follow-up data will be collected, including menstrual flow, ultrasound findings of intrauterine adhesions, endometrial condition, whether intrauterine adhesion surgery was performed, and intrauterine adhesion score.

5.7 Pregnancy outcome data collection: pregnancy rate after 1 year of trying to conceive ; miscarriage rate, premature birth rate, full-term birth rate, stillbirth rate, and stillbirth rate in subsequent pregnancies.

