9.2 Bias Control

The clinical research process strictly follows standard operating procedures, clearly defining pre-clinical research training, quality control, and other aspects.

All research institutions conducted their studies concurrently, implementing a unified clinical research protocol.

Before a clinical study begins, training should be provided on the clinical study protocol and standard operating procedures, especially on ultrasound report content, perioperative management, surgical procedure specifications, and surgical records.

The clinical research process includes monitoring and accountability procedures.

By controlling bias through the above process, research error can be reduced.

9.3 Pre-clinical training: Before a clinical trial, standard operating procedures should be developed in accordance with the clinical trial protocol, and all researchers participating in the trial should be trained on the clinical trial protocol, standard operating procedures, etc., to ensure consistency in all procedures during the trial; training should also be provided on ultrasound reporting standards, surgical operation standards, etc.; and training plans and records should be kept.

9.4 Research Quality Control: All researchers participating in the clinical trial should complete training on the clinical trial protocol, standard operating procedures, and other relevant documents, and strictly adhere to the provisions of these documents during the trial. Training should also be provided on ultrasound reporting standards and

surgical procedure standards. The lead institution will assign qualified monitors to conduct on-site monitoring visits to the clinical trial facility at different stages of the clinical trial to ensure that the clinical trial is conducted in accordance with relevant laws and regulations, the clinical trial protocol, and standard operating procedures.

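### The protocol's two numeric beta-HCG limits (below 50 and above 100) are printed in mmol/L, a unit impossible for HCG, and the intended unit is not given (minor)

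*Protocol*

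**What the plan says.** Protocol 4.1.2 (Expectant Treatment Group) lists four criteria that define when a woman under expectant management has reached the planned time for surgery. The first, with the start of the second, reads "Blood β -HCG <50mmol / L; 2) Ultrasound measurement of the length from the internal cervical os to the fundus". The others concern uterine length, the interval since the previous surgery and the blood-flow grade.

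Protocol 4.2.3 (Postoperative management) sets the length of oral estradiol after surgery at 21 to 28 days. The longer course is attached to "HCG levels above 100 mmol /L, oral administration until 28 days post-surgery". The 21-day course is described only in words, with neither a number nor a unit.

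Elsewhere HCG appears without a unit. The follow-up rule in 4.2.3 is "once a week thereafter until normal". The background explains the benefit of waiting partly by saying that "serum HCG levels drop to low levels, reducing the difficulty of hysteroscopic surgery". Section 5.2 lists serum beta-HCG among the variables and, for the expectant group, asks for it at each follow-up examination.

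**The concern.** Both limits are decision thresholds in the operative treatment sections, not background remarks. A millimolar concentration suits small molecules such as glucose or electrolytes, but not a protein hormone. If the printed unit cannot apply, the reader has two numbers and no stated scale.

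The background gives falling HCG as a reason why delayed surgery should be easier and safer, and criterion 1 is the number that puts that reason into practice. At stake is whether someone holding only the protocol can tell what limit was meant.

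**Working it through.** The plan gives no calculation for these limits, so there is no figure of its own to reproduce. The check has three parts.

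**1. Can the printed values occur?**

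Inputs from the protocol: 50 mmol/L (4.1.2) and 100 mmol/L (4.2.3). Input not in the protocol: the molar mass of HCG, assumed to be 22,000 to 40,000 g/mol, a deliberately wide range running from the beta subunit to the whole hormone.

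Formula: g/L = (mmol/L ÷ 1,000) × molar mass in g/mol.

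| Limit | At 22,000 g/mol | At 40,000 g/mol |
|---|---|---|
| 50 mmol/L | 0.05 × 22,000 = 1,100 g/L | 0.05 × 40,000 = 2,000 g/L |
| 100 mmol/L | 0.10 × 22,000 = 2,200 g/L | 0.10 × 40,000 = 4,000 g/L |

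Every entry is more than the mass of a litre of water (about 1,000 g).

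The same check can be run without assuming the mass of HCG. Assume total serum protein of 60 to 80 g/L and ask how light a molecule would have to be for the limit to fit inside that total:

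- 50 mmol/L: 60 ÷ 0.05 = 1,200 and 80 ÷ 0.05 = 1,600 g/mol at most.
- 100 mmol/L: 60 ÷ 0.10 = 600 and 80 ÷ 0.10 = 800 g/mol at most.

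The assumed range for HCG starts at 22,000 g/mol, more than ten times the largest of these (22,000 ÷ 1,600 = 13.75). The conclusion does not depend on where in the range the true mass lies.

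**2. What do the limits do if taken literally?**

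- Criterion 1 (below 50 mmol/L): every woman meets it at every visit, so it never delays surgery. The other three timing criteria are untouched.
- Estradiol rule (above 100 mmol/L): no woman exceeds it, so it never selects the 28-day course. The difference between the two courses is 28 − 21 = 7 days.

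**3. Does anything in the text shown supply the unit or use the limits downstream?**

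- Unit: no. All other HCG mentions, in the background and in 4.1.2, 4.2.1, 4.2.3, 4.3 and 5.2 to 5.5, have no unit.
- Grouping: section IV.2 assigns women by the treatment plan they chose, not by HCG.
- Analysis: section 8 names t-tests, analysis of variance, rank-sum tests and χ² or Fisher tests, and uses neither limit.
- Sample size: section IV.3 uses only adhesion rates of 14.29% and 5.38%, type I error 0.05, power 90% and 20% dropout. With a two-sided test, equal groups and unpooled variance, n per group = (1.960 + 1.282)² × (0.1429 × 0.8571 + 0.0538 × 0.9462) ÷ (0.1429 − 0.0538)², which rounds up to 230, so 460 in total. Then 230 ÷ 0.80 = 287.5, rounded up to 288 per group, or 576. Both stated totals reproduce with no HCG input.

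**The case against.** The strongest reply is that this is a clerical slip, possibly from translation, that no clinician would act on. Staff would read 50 and 100 on the scale their laboratory reports. The treatment rules are also loose around both limits. Section 4.1.2 says "Research hospitals can adjust the surgical timing parameters according to clinical experience" and allows admission at any time on the physician's assessment, while 4.2.3 permits adjustments to the estradiol regimen. Most of this stands, and it is why the point is minor and claims no harm. It does not remove the error: the same unit appears in two separate sections with different numbers, which makes a fault in reading the PDF unlikely, and permission to adjust a limit presupposes that the default can be read.

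Four stronger readings may tempt a reader, and the documents do not support them.

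- *That hospitals worked to different limits because their laboratories use different units.* Nothing in the protocol says that their units differ.
- *That the recorded HCG data are unusable.* Sections 5.1 to 5.5 are variable lists in which no measurement carries a unit, and "ultrasound data from each follow-up examination should be collected" is an instruction on what to gather. The case report form is a separate document that is not shown.
- *That the permission to adjust contradicts the bias-control statement* in 9.2, "All research institutions conducted their studies concurrently, implementing a unified clinical research protocol". A protocol that openly states a permission is still one protocol, so there is no contradiction.
- *That the four-week interval in criterion 3 cannot be checked.* Section 5.2 collects "gestational age at termination; time of termination" and 5.4 the date of surgery. Any remaining gap is conditional and would be inferred from a variable list, not from the form.

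A descriptive tabulation of how many women met the timing criteria might be useful, but such content is commonly left to a statistical analysis plan, and its absence here is no fault.

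**Conclusion.** Wrong as written, minor. Two decision limits, one of them one of the four timing criteria, carry a unit that HCG cannot have. Literally read, neither separates patients, and no text shown gives the intended unit. The impossibility rests on an assumed molar mass of 22,000 to 40,000 g/mol and holds across that whole range. An international-unit activity scale is the likely intention, but that is an inference that only the sponsor can confirm.

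A reader might go further and conclude that the treatment comparison is compromised or that women were operated on too early. The protocol does not support either: group membership, the primary comparison of adhesion incidence and the sample size (460, 576 and 600) do not depend on these limits, and the literal reading is not one that clinicians would be expected to apply. What is lost is that the protocol alone does not tell a reader or a new site which limits were meant.

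**What to change.** Restate the limit of 50 in 4.1.2 and the limit of 100 in 4.2.3 in the intended activity unit, after the sponsor has confirmed that unit against the lead hospital's source data. Section 4.1.2 says the timing criteria came partly from that hospital's earlier patients, so the source should be available. Use the same unit for recorded beta-HCG values.

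The cost is two unit corrections, one consistent unit for the recorded values and one look-up by the sponsor. No test, visit, analysis or sample-size figure changes, and the hospitals' freedom to adjust the timing parameters stays as it is.

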IV. Research Design

1. Research Subjects

who were diagnosed with retained products of pregnancy by ultrasound at outpatient clinics of various research units between June 2022 and June 2024, and who met the inclusion criteria but did not meet the exclusion criteria, were all enrolled consecutively.

Inclusion criteria: age 18-45 years, clinical diagnosis of retained products of conception, and ultrasound showing a lesion with a maximum diameter ≥ 0.5 cm.

Exclusion criteria: 1) Active bleeding requiring immediate surgical intervention; 2) Significant infection; 3) Severe organ dysfunction, including coagulation disorders.

Note: Patients with cervical tissue impacted in the cervical canal who have undergone clamping treatment and do not meet the exclusion

criteria can be included in this study;

2. Grouping

Because there is currently no unified treatment plan for retained products of pregnancy in uterus, the timing of active surgical evacuation versus expectant management until the planned surgery remains controversial, and the optimal timing for surgical evacuation is not uniform. In clinical practice, physicians, based on fully informed consent, choose active surgical treatment or expectant management according to the patient's wishes, and perform surgery when necessary. This study does not interfere with patient treatment; it only designs and collects relevant data in advance. No additional examinations or tests are performed on patients during the study process, and all procedures are conducted according to standard clinical practice. After treatment, patients are divided into an active surgical group and an expectant management group based on their chosen treatment plan, and data are statistically analyzed.

3. Sample size and allocation

The sample size was determined based on the incidence of intrauterine adhesions, the primary outcome measure. According to previous research results, the intrauterine adhesion rate in the expected group was 5.38%, and the intrauterine adhesion rate in the patients undergoing active surgery was 14.29%. The Type I error was 0.05, the power was 90%, and the sample size was calculated using PASS to obtain a total of 460 cases. Based on a 20% follow-up dropout rate, the sample size was calculated to be 576 cases. It is expected that 600 cases will be included, with 120 cases from the lead institution and an average of 40 cases from the other 12 research institutions.

4. Research Process

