4.1 Pre-hospitalization treatment

4.1.1 Active surgery group: Patients were admitted directly after enrollment and were scheduled to undergo hysteroscopic removal of pregnancy tissue.

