4.3 Data collection process

4.3.1 Outpatient data collection: The patient's first outpatient visit data and each outpatient follow-up visit data include main symptoms, blood β -HCG, ultrasound and infection-related indicators.

4.3.2 Data collection for inpatient surgery includes: preoperative symptoms; serum β -HCG, ultrasound and infection-related indicators; surgical data; and postoperative medication.

4.3.3 Follow-up after surgical treatment:

(1) If the ultrasound examination 3 days after the operation shows no pregnancy residue or the diameter of the residue is less than 0.5cm, follow up by phone or WeChat 1 month later to ensure that the patient's menstruation is over and to have a follow-up examination of β -HCG, ultrasound and other indicators at the outpatient clinic to determine whether the treatment has ended.

(2) If the ultrasound examination on the 3rd day after surgery shows that the

diameter of the retained pregnancy tissue is greater than 0.5cm, follow up by phone or WeChat half a month later to ensure that the patient goes to the outpatient clinic on schedule for β -HCG, ultrasound and infection indicators, and to determine the subsequent treatment plan.

4.3.4 Data collection after treatment: Menstrual flow, ultrasound findings of intrauterine adhesions, and endometrial thickness were collected during outpatient follow-up examinations three times after the end of treatment.

4.3.5 Data collection on reproductive outcomes: For patients who wish to have children, follow-up by telephone will continue every 3 months. If the patient has not become pregnant after 1 year of follow-up, the follow-up will be terminated. If the patient becomes pregnant within 1 year, follow-up will continue until the pregnancy is terminated, including whether there is spontaneous abortion, premature birth, full-term birth, stillbirth, or stillbirth.

5. Data Collection

5.1 General information: age, parity, number of previous intrauterine procedures, history of intrauterine adhesions, occupation, and education level.

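### Women who already meet the surgical-timing criteria at enrolment enter the adhesion comparison unseparated; record this status at baseline and stratify by it

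*Protocol*

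**What the plan says.** Eligibility (Protocol, IV.1 Research Subjects) rests on "age 18-45 years, clinical diagnosis of retained products of conception, and ultrasound showing a lesion with a maximum diameter ≥ 0.5 cm". The exclusions are active bleeding that needs immediate surgery, significant infection and severe organ dysfunction. HCG, uterine length, flow grade and time since termination or last operation play no part.

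For the active surgery group (4.1.1): "Patients were admitted directly after enrollment and were scheduled to undergo hysteroscopic removal of pregnancy tissue".

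The expectant group (4.1.2) waits until four criteria are met: HCG below 50, a length from internal os to fundus of at most 6 cm, at least 4 weeks since the previous surgery, and flow grade 1-3. Then: "Patients who reach the predetermined surgical timing will be hospitalized, undergo relevant examinations, and undergo hysteroscopic removal of the pregnancy tissue". No minimum wait is given. The same section adds: "Research hospitals can adjust the surgical timing parameters according to clinical experience".

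The hypothesis in the background text is that "in the absence of infection and active bleeding, expectant management should be maintained until the appropriate surgical time". Section IV.2 forms the two groups after treatment, by chosen plan. Section 8 compares them whole.

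**The concern.** The study asks whether waiting for the right surgical moment reduces intrauterine adhesions. A woman who is already at that moment when she enrols has little or nothing to wait for. On a literal reading, both plans take her to hysteroscopy promptly.

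Such women are plausible. The background text says "when curettage is performed 1-3 months after termination of pregnancy, serum HCG levels drop to low levels, reducing the difficulty of hysteroscopic surgery", and a woman first diagnosed that late is eligible. That sentence concerns when surgery is done, however. It does not say how many women present late with all four criteria met.

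Two consequences follow if they are not rare. Spread evenly over the groups, they shrink the observed adhesion difference. Spread unevenly, they confound it in either direction, because the background text links low HCG to easier surgery and fewer adhesions, and a large uterus and rich blood supply to repeat curettage. Because groups are formed after treatment, the label of a promptly operated woman is also less secure than one written down at enrolment.

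**Working it through.** **Inputs from the protocol (IV.3).** Adhesion rates 14.29% (active) and 5.38% (expectant), alpha 0.05, power 90%, 460 evaluable, 20% dropout giving 576, 600 to be enrolled. Two-sided testing and 1:1 allocation are assumed; they reproduce the stated total.

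**The plan's own figure.** n per group = (1.960 + 1.282)² × [0.1429×0.8571 + 0.0538×0.9462] / (0.0891)² = 10.507 × 0.17339 / 0.0079388 = 229.5, so 230 per group and 460 in total. Dropout: 230/0.8 = 287.5, so 288 per group and 576. Both figures are reproduced. With 600 × 0.8 = 480 evaluable (240 per group), the pooled two-sided z-test has 90.9% power.

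**Assumed, not in the documents.** The share f of women already at the timing, and their adhesion risk r.

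**Even spread, no effect in women already at the timing, planned rates holding only for the others.** The rates become f·r + (1−f)·14.29% and f·r + (1−f)·5.38%, so the difference is (1−f) × 8.91 points. Power is shown for r from 14.29% down to 0%. The last column is the test among women not yet at the timing.

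| f | Difference (points) | Power, all women | Evaluable, not yet at timing | Power, not yet at timing |
|---|---|---|---|---|
| 2% | 8.73 | 89.5-90.2% | 470 | 90.3% |
| 5% | 8.46 | 87.2-89.2% | 456 | 89.4% |
| 10% | 8.02 | 82.7-87.4% | 432 | 87.7% |
| 20% | 7.13 | 71.5-82.9% | 384 | 83.7% |
| 30% | 6.24 | 58.3-77.2% | 336 | 78.6% |

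**Same, but the planned rates already describe the mix.** Power in all women stays at 90.9%, so nothing is lost against plan. Among women not yet at the timing the difference is 8.91/(1−f) = 9.90, 11.14 or 12.73 points at f = 10, 20 or 30%. Power there is 91.2-94.5%, 91.7-97.4% or 92.2-99.2%.

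**Uneven spread, no true timing effect.** Risk is set at 5.38% in women at the timing and 14.29% in the others, with the others split evenly over 480 women. Example, f = 20% and a 75/25 split of the 96 women at the timing:
- expectant: (72×5.38% + 192×14.29%)/264 = 11.86%
- active: (24×5.38% + 192×14.29%)/216 = 13.30%
- false difference 1.44 points

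| f | 60/40: false difference, rejection rate | 75/25: false difference, rejection rate |
|---|---|---|
| 5% | 0.17 points, 5.0% | 0.42 points, 5.2% |
| 10% | 0.32 points, 5.1% | 0.80 points, 5.8% |
| 20% | 0.57 points, 5.4% | 1.44 points, 7.7% |
| 30% | 0.75 points, 5.8% | 1.91 points, 10.2% |

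Reversing the split reverses the sign. Within each stratum the rates are equal by construction, so a comparison stratified by baseline status removes this false difference.

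**Can the status be reconstructed later?** Partly. Section 4.3.1 says the "first outpatient visit data and each outpatient follow-up visit data include main symptoms", along with HCG and ultrasound, and section 5.2 lists os-to-fundus length and blood flow. For the 4-week criterion, section 5.1 lists only "age, parity, number of previous intrauterine procedures, history of intrauterine adhesions, occupation, and education level". Section 5.2 adds the time of termination. The date of the last intrauterine operation before enrolment is not listed.

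**The case against.** The strongest reply is that the share of such women is unknown and may be tiny. That stands. At 5% the test in all women is at most 2.2 points below the test in women not yet at the timing, and at 2% at most 0.8 points.

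The second reply is that the two plans are not identical for these women. The Project Overview describes surgery only when necessary. Section 4.1.2 includes an outpatient work-up, oestradiol and ultrasound every 2-3 weeks, and allows for spontaneous expulsion. Some delay and some benefit are therefore possible, and the absence of any effect in these women is an assumption. If they had more than about 54-66% of the full relative reduction, leaving them out would cost power. This also stands.

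The third reply is that confounding by patient choice is general in this design and that adjustment is commonly left to an SAP. That is true of the method of adjustment. But an SAP can use only what was recorded, and neither a timing status on common values nor the date of the last operation is collected.

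A reader might infer that the sample size is wrong, or that women already at the timing should be removed from the primary population. The documents support neither. The planned rates come from earlier results that may already include such women. Removing them would narrow a consecutive real-world study. It would leave 432, 384 or 336 evaluable women (f = 10, 20 or 30%) against the planned 460, and would misclassify women at sites that use adjusted criteria.

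**Conclusion.** The point holds as a gap in design and recording. Sections IV.1, 4.1.1 and 4.1.2 together let women with little or no timing contrast into the primary comparison, and sections IV.2 and 8 do not separate them.

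Its size cannot be fixed from the documents. Over an assumed share of 10-30%, power in all women with 480 evaluable lies between 58.3% and 87.4% if the planned rates hold only for the other women, and is unchanged at 90.9% if those rates already describe the mix. Uneven spread gives a false difference of 0.3 to 1.9 points and a rejection rate of 5.1-10.2%. The top of that range needs a 30% share, a 75/25 split and the whole planned 8.91-point difference attributed to baseline status. At about 5% or less the effect is negligible. This is a cheap improvement worth making, not a flaw that invalidates the design.

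**What to change.** - At the enrolment visit, before treatment, record the chosen plan and whether the section 4.1.2 criteria are already met.
- Use one set of reference values at every site. Where a hospital has adjusted its criteria, also record the status on its own values.
- Correct the printed HCG unit (mmol / L). IU/L is the likely intention, but the sponsor must confirm it. State how the 4-week criterion counts for a woman with no previous operation.
- Add the date of the last intrauterine operation to the CRF.
- Keep all enrolled women in the primary population and stratify or adjust the adhesion comparison by baseline timing status.
- Prespecify the comparison in women not yet at the timing as a key supporting analysis, and report women already at the timing separately.

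The cost is one enrolment record, one CRF date and a little more analysis. No extra test or patient is needed, since HCG, ultrasound, uterine length and flow are already collected. The supporting analysis has fewer women: about 432, 384 or 336 of 480 at the assumed shares of 10, 20 or 30%. Other confounding by patient choice remains.
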